Following extubation, patients will be randomly assigned to Study group 1 or 2, or to Control group at 1:1:1 ratio. Blocks of 3 numbers will be consecutively drawn from a sequence of 99 unique random numbers (range, 1-99). Random numbers will be generated by using Research Randomizer version 4.0 (www.randomizer.org). Upon patient enrollment, attending investigators will receive text message on their mobile phone devices. The text message will display the patient's code number and group.

Patient monitoring and data collection

Continuous patient monitoring will include electrocardiographic lead II, intra-arterial pressure, SpO₂, and respiratory rate.

Data on patient characteristics, including the European System for Cardiac Operative Risk Evaluation (EUROSCORE) II will be collected at baseline. Data collection time points for SpO₂, respiratory rate, PaO₂/FiO₂, comfort with respect to dyspnea and respiratory support modality (VAS score^{34,35,36}), accessory muscles' use, arterial pressure and heart rate, vasopressor support, and core body temperature will be as follows: within 30 min of extubation (baseline) and at 1, 2, and 4 hours, and every 4 hours onwards until 48 hours postextubation. Fluid balance of the first 24 and 48 hours postextubation will be recorded as well.

Adverse events/clinical course complications (e.g. hypoxemia and/or need for re-intubation, arrhythmias such as atrial fibrillation, occurrence of delirium,^{37,38,39,40,41} epileptic seizures, surgical re-exploration due to bleeding, ICU readmission, chest wound infection), and any patient discomfort/intolerance related to HFNC will also be recorded.

Management of respiratory support

Patients will be assessed for gradual reduction in the intensity of respiratory support or need for support escalation every 4 hours postextubation. Gradual weaning from NHF will be accomplished by FiO₂ decrease to 0.5, followed by gas flow decrease to 30 L/min NHF weaning target will include an FiO₂ of 0.4 and a gas flow of 20 L/min.^{8,42} If at an NHF FiO₂ of 0.4 and a flow rate of 20 L/min, SpO₂ can be maintained at >92% and respiratory rate remains within 12-20 breaths/min for ≥ 2 hours, patients will be switched to a Venturi mask providing an FiO₂ of 0.4). In the Control group, a reduction of FiO₂ to 0.4 (via a Venturi mask) will be sought. Patients of all groups fulfilling the aforementioned SpO₂/respiratory rate criteria for at least 4 hours while receiving an FiO₂ of 0.4 via a Venturi mask will be considered for ICU discharge. As part of standard practice, patients will be scheduled for twice-daily physiotherapy.

Regarding treatment escalation in Study groups, if SpO₂ drops to $\leq 92\%$ for at least 5 min at a gas flow of less than 60 L/min, gas flow will first be increased by 5-10 L/min.⁴ Next, if SpO₂ remains at or below 92%, FiO₂ will be increased⁴³ to achieve an SpO₂ of >92%. In the Control group, an SpO₂ of 92% or less for at least 5 min will be initially treated with FiO₂ increase. In all groups, persistent and/or worsening hypoxemia will be ultimately treated with non-invasive mechanical ventilation and/or reintubation and initiation of invasive mechanical ventilation.

Treatment decisions and premature discontinuation of physiological data collection

Changes in the intensity and/or modality of respiratory support will ultimately be decided by the primary attending physicians of the patients. Initiation of mechanical ventilation or ICU discharge within 48 hours of extubation will result in discontinuation of the pre-specified 4-hourly patient data collection.

Outcome measures

Primary: Occurrence of treatment failure; regarding the NHF groups, this will be further specified as inability of weaning from NHF (i.e. inability of achieving successful weaning from NHF) according to study protocol.

Secondary: 1] Successful maintenance of an SpO₂ of >92% and a respiratory rate of 12-29 breaths/min at the specified time points of follow-up; the term "successful" corresponds to the absence of any escalation of respiratory support above its initially specified level for each one of the Study groups and the Control group; 2] PaO₂/FiO₂ at the specified time points of follow-up; 3] Any use of accessory respiratory muscles at the specified time points of follow-up; and 4] Patient comfort as regards dyspnea, and patient tolerance of NHF support according to a VAS score.

Additional: 1] Length of cardiothoracic ICU stay; 2] Length of hospital stay; 3] ICU and in-hospital mortality; and 4] Adverse events (e.g. hypoxemia and/or need for re-intubation, arrhythmias such as atrial fibrillation, occurrence of delirium, epileptic seizures, surgical re-exploration due to bleeding, ICU readmission, chest wound infection), and any patient discomfort/intolerance related to NHF.

Sample Size and Power Analysis

The proposed sample size is based on a formal power calculation, i.e. an *apriori* power analysis, which is an efficient method of controlling statistical power before a study is actually conducted; for power analysis, G*Power 3 software was used.⁴⁴ We predict a treatment failure rate of 15% in the 2 Study groups (10% in Study group 1 and 20% in Study group 2) and a failure rate of 51% in the Control group. The predicted NHF-to-control treatment failure ratio of 0.29 corresponds to the lower limit of the 95% confidence interval (CI) of a previously determined "NHF vs. Control" odds ratio for support escalation.²⁵ For alpha=0.05 and power=0.80, 63 patients (n=21 per group) will be required. However, we cannot exclude a potential risk for dropouts and/or missing data. To compensate for such a risk, we propose the ultimate enrolment of 99 patients (i.e. n=33 per group), in order to achieve an alpha value of 0.05, a power of 0.96, and a "safety margin" of 57% as regards possible dropouts and/or missing data. The predicted study enrollment rate is 40-50 patients per year.

Interim Analysis and Data Monitoring

At 1 year following study start, an interim analysis will be conducted by Drs. [name] (Senior Consultant in Intensive Care Medicine, First Department of Intensive Care Medicine, University National and Kapodistrian University of Athens Medical School, Evangelismos General Hospital, Athens, Greece) and [name] (Senior Consultant, Department of Cardiac Surgery, Evangelismos General Hospital, Athens, Greece). The analysis will be focused at evaluating and confirming 1) the safety of the study protocol (including any reported adverse events); 2) the applicability of the study protocol (including an assessment of the achieved level of adherence to the specified investigational interventions); 3) the completion of the attached study forms as mandated by the study protocol; and 4) the safety of the electronically stored patient data. Actions related to the

aforementioned points 1-4 may be undertaken at the discretion of the aforementioned study-independent Colleagues at any time point throughout the conduct of the current study. Data quality and completeness will also be evaluated by the aforementioned study-independent Colleagues after the completion of the study.

Statistical Analysis Plan

Analyses will be performed according to intention-to-treat principle. Distribution normality will be determined by Kolmogorov Smirnov test. Continuous variables will be presented as mean \pm SD or median (IQR). Qualitative variables will be presented as number (percentage). Percentages will be compared by Fisher's exact test.

The effect of group on treatment failure will be assessed using multivariable Cox regression. Hazard ratios and respective 95% confidence intervals will be determined for group, EuroSCORE II (which includes age and gender as risk factors), body mass index, cardiopulmonary bypass time, and duration of postoperative sedation and pre-extubation assisted and spontaneous breathing.

$\text{SpO}_2 > 92\%$, and respiratory rate within 12- 20 breaths/min will be assessed as binary outcomes (i.e. maintenance vs. no maintenance of SpO_2 /respiratory rate above/within the aforementioned limits without escalation of support above initial level) Logistic regression models will be fitted using group, time, and group*time interaction as explanatory variables. Changes in oxygenation, VAS comfort scale score, and non-outcome follow-up variables (i.e. PaCO_2 , arterial blood lactate, hemoglobin concentration, hemodynamic variables, temperature, and vasopressor support) will be analysed by using linear mixed models analyses with group, time, and group*time, as fixed factors, and "patients" as random factor. Dependent variables with skewed distributions will be log-transformed. The Bonferroni correction will be applied on the P values of pairwise comparisons.

Two-tailed P values will be reported. Statistical significance will be accepted at 0.05. Analyses will be conducted using SPSS version 21 or any subsequent version (IBM corporation, Armonk NY).

Importance of the study

The early use of NHF in post-extubated cardiac surgery patients may potentially assist them in achieving a faster recovery by providing higher and more stable levels of humidified and warmed oxygen while supporting the respiratory effort through positive airway pressures. This could also be associated with a reduction in the risk for postoperative pulmonary complications. This study may also help in determining the best level of initial NHF support in cardiac surgery patients with postoperative hypoxemia.

Study Funding Statement

The AIRVO™ 2 (Fisher & Paykel Healthcare, Auckland New Zealand) device (with built in flow generator) is already available at our institution. Regarding disposables, we estimate a total cost of 90 Euro per patient (heated humidifier, 60 Euro; Nasal prongs, 15 Euro; compatible opti flow circuit, 15 Euro. The maximum cost of disposables is estimated at 5940

Euro (+24% value added tax). This cost will be covered by the Special Account for Research Funds, University of Athens Medical School, Athens, Greece. The current study will not cause any financial burden to Evangelismos Hospital.

Doctoral Thesis

This study corresponds to the Doctoral Thesis of [name].

References (updated 14/09/2018)

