Treatment failure will be defined as any crossover from one treatment to another due to patient's respiratory distress and discomfort. To be more specific, switch of gas flow from 40L/min to 60L/min, crossover from either NHF group to standard practice (Venturi mask) or need for more advanced respiratory support such as non-invasive ventilation or invasive mechanical ventilation, inability to reverse FiO_2 and/or gas flow escalation above initial settings within 48 hours of its initiation. Escalation reversal will be defined as return to initial (or lower) FiO_2 and/or gas flow for ≥ 4 hours.

Inclusion criteria will be: Cardiac ICU adult patients > 18 years after elective or urgent cardiac surgery having passed a successful Spontaneous Breathing Trial (SBT) with T-piece and $\text{FiO}_2=0.6$. A successful SBT will have to fulfil the following criteria^{31, 32, 33} respiratory rate: 12-29 breaths/min, $\text{SpO}_2 > 92\%$, $\text{PaCO}_2 < 45\text{ mmHg}$, heart rate <120/min, and systolic arterial pressure of 90-160 mmHg while receiving norepinephrine at a rate of 0.00 $\mu\text{g}/\text{kg}/\text{min}$ to 0.15 $\mu\text{g}/\text{kg}/\text{min}$. The most important inclusion criterion is residual respiratory impairment at the end of SBT defined as $\text{PaO}_2/\text{FiO}_2 < 200 \text{ mmHg}$ while receiving $\text{FiO}_2=0.6$. The decision to extubate under these specific conditions will be made by the attending physicians.

The exclusion criteria will comprise: 1) Obstructive Sleep Apnea Syndrome supported by a continuous positive airways pressure device, 2) preoperative diagnosis of Chronic Obstructive Pulmonary disease, 3) patients already tracheostomized, 4) do not resuscitate status, 5) Glasgow Coma Scale score <13, 6) Insufficient knowledge of Greek Language , and 7) any visual or hearing impairment.

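### Relapse after weaning from NHF has no single primary-outcome score, and the same relapse can be scored differently by arm depending on the device chosen

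*Combined protocol and SAP*

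**What the plan says.** Methods gives the general rule: "Treatment failure will be defined as any crossover from one treatment to another due to patient's respiratory distress and discomfort". It then lists specific cases: a flow switch from 40 to 60 L/min, "crossover from either NHF group to standard practice (Venturi mask) or need for more advanced respiratory support" (non-invasive or invasive ventilation), and failure to reverse FiO2 and/or "gas flow escalation above initial settings within 48 hours of its initiation". Reversal means at least 4 hours back at the initial level or lower. A move from Venturi back to NHF is not in the list.

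Outcome measures keeps treatment failure as the primary outcome, but adds for the NHF arms only: "regarding the NHF groups, this will be further specified as inability of weaning from NHF (i.e. inability of achieving successful weaning from NHF". It sets no length of time off NHF for weaning to count as successful, and it has no control-arm counterpart.

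Management of respiratory support ends NHF weaning as follows: after at least 2 hours meeting criteria at FiO2 0.4 and 20 L/min, "patients will be switched to a Venturi mask providing an FiO₂ of 0.4". The protocol summary that precedes Study Eligibility Criteria also lets the physician go to Venturi from 25 to 30 L/min. The escalation steps for the study groups are written for a patient on NHF gas flow. For control: "In the Control group, an SpO₂ of 92% or less for at least 5 min will be initially treated with FiO₂ increase". In every group, persistent hypoxemia ends in non-invasive ventilation and/or reintubation. Changes of modality rest with the attending physicians, and Methods states that the study is not blinded.

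**The concern.** Once an NHF patient is on Venturi at FiO2 0.4, that patient receives the same support as a weaned control patient. A fall in saturation at that point is the same clinical event in all three arms, yet the text does not score it by one rule. In an NHF arm the score depends on which section governs and on whether the physician goes back to NHF or raises the Venturi FiO2. In control, the FiO2 rise is the first step, and up to 0.6 it does not exceed the initial setting.

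Two things are at stake. The primary comparison could carry a difference created by the definition rather than by the treatment. The choice between readings could also be made after the data are seen. The Cox model in the Statistical Analysis Plan needs an event and an event time for each patient, so someone must decide whether a relapse is an event at that hour or no event.

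**Working it through.** **Step 1: set the passages side by side.** Take a patient on Venturi at FiO2 0.4 after weaning.

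| What happens next | Methods definition | NHF-only wording in Outcome measures |
|---|---|---|
| NHF patient returned to NHF for distress, at or below initial settings | Failure by the general sentence; not in the specific list; not above initial settings | Success if reaching the switch is enough; failure if success means staying off NHF |
| NHF patient, Venturi FiO2 raised to at most 0.6 | Not a failure | Not a failure: still off NHF |
| NHF patient given NIV or reintubated | Failure | Not plainly a failure to wean |
| Control patient, Venturi FiO2 raised to at most 0.6 | Not a failure | Does not apply |
| Control patient given NIV, reintubated, crossed over for distress, or above FiO2 0.6 and not reversed in time | Failure | Does not apply |

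Row 1 has two defensible scores. Rows 1 and 4 can be the same clinical event with different scores.

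**Step 2: reproduce the plan's figure.** Sample Size and Power Analysis predicts failure rates of 10%, 20% and 51%, alpha 0.05, power 0.80, and 63 patients. A three-group chi-square test (2 df) has mean rate (0.10 + 0.20 + 0.51)/3 = 0.27 and effect size w = 0.393. The smallest N with 80% power is 63 (power 0.804). At N = 99 power is 0.948. Pooled NHF 15% against control 51%, 66 vs 33, gives 0.963 by the normal approximation and 0.952 by exact two-sided Fisher test. The plan states 0.96. There is no arithmetic error in the plan here.

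**Step 3: show the possible size.** The relapse rate is not in the documents. Assume that a share r of otherwise successful NHF patients relapse, with r from 5% to 20%. On the plan's rates, 85% of 66, about 56 patients, are otherwise successful, so r gives about 3 to 11 patients.

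- One-sided scoring: NHF rate = 0.15 + 0.85r; control stays at 0.51.
- Common scoring: the same NHF rate; control = 0.51 + 0.49r.

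| r | NHF rate | Risk ratio vs 51% | Fisher power, one-sided scoring | Control rate, common scoring | Fisher power, common scoring |
|---|---|---|---|---|---|
| 0 | 15.0% | 0.29 | 0.952 | 51.0% | 0.952 |
| 5% | 19.3% | 0.38 | 0.876 | 53.5% | 0.918 |
| 10% | 23.5% | 0.46 | 0.754 | 55.9% | 0.875 |
| 20% | 32.0% | 0.63 | 0.405 | 60.8% | 0.737 |

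At r = 10% the total loss is 0.952 − 0.754 = 0.198. Common scoring would cost 0.952 − 0.875 = 0.077. The remaining 0.121 comes from counting relapse in the NHF arms alone.

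These figures use a pooled two-group Fisher test for scale. The planned primary analysis is a Cox model.

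**The case against.** The strongest reply is that the Methods definition treats like actions alike. A Venturi rise from 0.4 to 0.6 is not a failure in any arm, and a distress-driven move to NHF is a crossover in any arm. A reader might infer that a control relapse can never be a failure. The documents do not support that: NIV, reintubation, a distress-driven crossover, or FiO2 above 0.6 that is not reversed all count. The notes to the diagrammatic procedure even describe control patients on a nonrebreathing mask at FiO2 0.9 and how that is reversed.

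A reader might also infer that Outcome measures settles the weaned patient as a success. It does not. It keeps treatment failure as the outcome, and a patient who must go back on NHF can fairly be read as not successfully weaned; on that reading the two sections agree. Nor is a return to NHF in the specific list, and no visible text directs it.

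The power figures are also open to challenge. The model sends every relapse back to NHF, although an FiO2 rise on Venturi is equally possible, and it counts none in control. The predicted 15% may already include such relapses. The flow diagram is not shown and may settle the step.

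All of this narrows the point. What remains is that two readings are open for one event, neither section chooses between them, and the usual control response to that event is not a failure.

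**Conclusion.** The point holds as an inconsistency in the outcome definition that can produce arm-dependent scoring. It concerns relapse managed at or below the initial support level. It also touches NIV or reintubation after weaning, which fails under Methods but is not plainly an inability to wean.

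The size is unknown because the relapse rate is unknown. The fall in Fisher power from 0.95 to 0.88–0.41 is an upper bound for an assumed 5–20% relapse. It requires that every NHF relapse counts, no control relapse counts, and none is already in the 15%. Counted in all arms at the same rate, power is 0.92–0.74. A reader might infer that the planned effect could be reversed. The figures do not show that: at 20% relapse with one-sided scoring the risk ratio is still 0.63, so the effect is diluted. The conclusion is subject to what the missing diagram says.

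**What to change.** Reconcile Methods and Outcome measures into one failure definition applied identically in all three arms, before the data are analysed. This changes scoring only, not how patients are managed.

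- Judge relapse after weaning against the arm's initially specified support level. The first secondary outcome already uses this yardstick in every arm.
- Count NIV or invasive ventilation for respiratory reasons as failure in every arm, whether or not weaning had been reached, within a stated time window.
- Record relapse at or below the initial level in all arms and report it separately, so that it is visible although outside the primary outcome.
- Add one sensitivity analysis that counts such relapse as failure in all three arms.

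The cost is a paragraph of wording and one extra analysis. There is a data cost too: the 4-hourly readings stop at ICU discharge, which may be considered after 4 hours on Venturi at FiO2 0.4, so later relapses within the window need another source. If the flow diagram already settles the step, its rule should be written into the outcome definition.

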Studies applying NHF immediately after extubation in cardiac surgery patients revealed better oxygenation and less need for advanced methods of respiratory support compared to conventional oxygen devices^{25,26}, and similar results compared to noninvasive ventilation²⁷. However, Zochios et al,²⁸ summarized all the available up to date data of NHF compared to conventional oxygen devices and non-invasive ventilation in patients undergoing cardiothoracic surgery and they did not find any further benefit by NHF use. The aforementioned discordant results could be explained by the differences in the studied populations and NHF flow settings. The proposed initial flow rate differs among the studies, with some authors^{2,4} suggesting initial lower flows (35-40 L/min) that will be better tolerated by the patients and others suggesting initial maximal flows (60 L/min) to rapidly relieve dyspnea and prevent muscle fatigue.^{29,30}

Aim

The primary goal of the study is to evaluate the efficacy of NHF versus conventional oxygen systems as regards treatment failure (as defined below) and respiratory parameters [respiratory rate, PaO_2 / (fraction of inspired oxygen) FiO_2 , peripheral oxygen saturation (SpO_2), use of accessory muscles, and dyspnea and comfort as regards the technique of respiratory support by using a visual analogue scale (VAS) after the extubation of cardiac surgery patients. An additional major goal of the study is to compare two different initial NHF flows of 60 L/min and 40 L/min, intensive care unit (ICU) Length of Stay, Hospital Length of Stay, rates of ICU re-admission and re-intubation and any other respiratory / non-respiratory complications and adverse events. The rate of failure of the initial treatment will be determined as the primary study outcome.

Methods

This is a prospective, non-blinded, randomized study in post-extubated cardiac surgery patients. The study population will consist of three patient groups: The first group (Study Group 1) will include patients on NHF with initial settings of $\text{FiO}_2=0.6$ and gas flow=60L/min. The second group (Study Group 2) will include patients on NHF with initial settings of $\text{FiO}_2=0.6$ and gas flow=40L/min. In the third group (control group) all patients will receive oxygen therapy according to the standard practice of our cardiac ICU department, i.e., Venturi mask with $\text{FiO}_2=0.6$ and flow of 15 L/min.

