Baseline measurements will be undertaken within 30 min after extubation. Subsequently, all patients will be assessed for downward titration of respiratory support at 1, 2 hours, and then, every 4 hours after extubation. Respiratory physiological follow-up will extend up to 48 hours after extubation. At the aforementioned follow-up time points, data collection will include SpO_2 , respiratory rate, $\text{PaO}_2/\text{FiO}_2$, comfort as regards dyspnea and respiratory support modality [visual analogue scale (VAS) score²⁴], accessory muscles' use, arterial pressure and heart rate, vasopressor support, and core body temperature. Fluid balance of the first 24 and 48 hours postextubation will also be recorded.

Gradual weaning from NHF support will include FiO_2 downward titration to 50%, followed by downward titration of gas flow to 30 L/min, aiming at a final wean-off goal of $\text{FiO}_2=0.4$ and gas flow=20 L/min (unless the attending physician decides to turn the patient to a Venturi mask from a gas flow of 25 to 30 L/min).¹² If at NHF $\text{FiO}_2=0.4$ and flow rate=20 L/min, pulse oximeter-measured, peripheral oxygen saturation (SpO_2) and respiratory rate can be respectively maintained above 92% and within 12 to 20 breaths/min for at least 2 hours, patients will be switched to conventional oxygen therapy with a Venturi mask ($\text{FiO}_2=0.4$). In the control group, downward titration of support will be aimed at Venturi mask $\text{FiO}_2=0.4$. Patients of all groups fulfilling the aforementioned SpO_2 /respiratory rate criteria for at least 4 hours while receiving an FiO_2 of 0.4 via a Venturi mask will be considered for cardiothoracic ICU discharge.

During the postoperative/postextubation period, respiratory support may be escalated to maintain an SpO_2 of >92% and a respiratory rate of 12-29 breaths/min. Changes in respiratory support level and/or modality will ultimately made and/or approved by the patients' primary attending physicians.

Study Eligibility Criteria

- Adult Cardiac ICU patients.

- Age of more than 18 years.
- After elective or urgent cardiac surgery.
- Successful spontaneous breathing trial with T-piece and an FiO_2 of 60% (eligibility criterion for extubation).
- $\text{PaO}_2/\text{FiO}_2$ of less than 200 mmHg (moderate hypoxemia – normal value \sim 500 mmHg)
- Hemodynamically stable, defined as systolic arterial pressure within 90 to 160 mmHg with or without low-to-moderate vasopressor support.

Exclusion Criteria:

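### Device discomfort or intolerance is a named event only for NHF, so it is prompted in two arms and unprompted in control; the item cannot support a comparison with the mask as written

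*Combined protocol and SAP*

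**What the plan says.** The Outcome measures section ends its Additional item 4, a list of example adverse events, with "and any patient discomfort/intolerance related to NHF". The section on patient monitoring and data collection closes its own adverse-event list in the same way: "any patient discomfort/intolerance related to HFNC will also be recorded". HFNC is used there for the same therapy. Secondary outcome 4 has a similar limit: "Patient comfort as regards dyspnea, and patient tolerance of NHF support according to a VAS score".

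No section names a corresponding item for the Venturi mask, or for the nonrebreathing mask that the notes to the diagrammatic SOP mention for escalated control patients.

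Other parts of the plan are not restricted to NHF:

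- The Aim lists comfort with the support technique among the NHF-versus-conventional comparisons.
- The monitoring section collects "comfort with respect to dyspnea and respiratory support modality (VAS score") on a schedule common to all arms. The second description of follow-up, just before the Study Eligibility Criteria, does likewise.
- The Statistical Analysis Plan models the VAS comfort score by group, time and their interaction, with no arm left out.
- The adverse-event SOP (sections 2.1 and 2.4) defines adverse events broadly and requires all of them to be recorded.

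The Statistical Analysis Plan names no test for the discomfort/intolerance item. It says only that percentages will be compared by Fisher's exact test.

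**The concern.** The trial sets out to compare NHF with a mask, and tolerance of the device is a natural part of that comparison. An event that staff are told to look for in two arms and not in the third will be found more often where it is sought. The trial is unblinded, so staff know which patients the instruction applies to.

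The outcome definition and the collection instruction carry the same restriction, so it is unlikely to be a slip in one sentence. If the item appears in a by-arm table, or falls under the general Fisher sentence, part or all of any excess in the NHF arms could come from how the event was collected. A reader of the results could not separate that from a real difference.

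**Working it through.** No figure in the plan rests on this point, so there is none to reproduce. The only inputs from the documents are 33 patients per arm (99 enrolled, 1:1:1), two-tailed P values, a 0.05 threshold and Fisher's exact test. The true intolerance rate q is not given. It is assumed equal in all arms and varied from 5% to 30%.

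**Step 1. What is collected, by arm**

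| Source | NHF 60 and 40 L/min | Control |
|---|---|---|
| Named discomfort/intolerance event | Prompted | Not named |
| General adverse-event recording | Yes | Yes, unprompted for the mask |
| VAS comfort at scheduled time points | Yes | Yes |
| Tolerance wording in secondary outcome 4 | Yes | Not named |

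The asymmetry lies in the first and last rows. The VAS does not fully close the gap. The SOP for rating breathing comfort scripts one question, scored 0 to 10, with anchors that describe ability to breathe. A patient who breathes easily but cannot bear the mask may still score well.

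**Step 2. Significance threshold in the limiting case (control records 0 of 33)**

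With k events among n NHF patients and none in control, the observed table has probability C(n,k)/C(n+33,k). The two-sided P value adds every table that is no more probable.

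- Pooled NHF, n = 66, k = 8: the observed table has probability 0.0335. The tables with 6, 7 or 8 of the 8 events in control add 0.0139 + 0.0016 + 0.0001. P = 0.049. At k = 7, P = 0.092. The threshold is 8 of 66.
- One NHF arm, n = 33, k = 6: P = 2 × 0.0122 = 0.024. At k = 5, P = 0.053. The threshold is 6 of 33.

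**Step 3. Chance of a false result that NHF is worse**

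Pooled: 1 − Σ(j = 0 to 7) C(66,j) q^j (1−q)^(66−j). One arm: the same with 33 patients and j = 0 to 5.

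| Assumed q, all arms | Expected NHF events (66q) | Pooled NHF vs control | One NHF arm vs control | Pooled, if all arms are counted alike (either direction) |
|---|---|---|---|---|
| 5% | 3.3 | 1.7% | 0.5% | 2.5% |
| 10% | 6.6 | 34% | 11% | 3.2% |
| 15% | 9.9 | 79% | 37% | 3.4% |
| 20% | 13.2 | 97% | 67% | 3.6% |
| 30% | 19.8 | about 100% | 96% | 3.8% |

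At 5% there are too few events to reach significance often, so the bias shows in the counts more than in the P value. From about 10% upward the false-positive rate is far above what identical recording gives.

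**Step 4. If control events are partly captured**

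Let general recording pick up a fraction c of the control events. The chance is then the sum of Bin(x; 33, cq) × Bin(y; 66, q) over tables that are significant with NHF higher. At q = 10%, 15% and 20%, c = one quarter gives about 15%, 31% and 47%; c = one half gives about 7%, 12% and 19%. The Step 3 figures for the NHF-only item are thus an upper bound that falls as capture improves.

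**The case against.** A reader might infer more than the documents support, namely that the control count is zero by definition, that the whole tolerance comparison is one-sided, or that the trial cannot say which device is better tolerated. The case against those readings is good.

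- **Comfort is compared in all three arms.** The VAS covers the support modality as well as dyspnea, is collected on a common schedule and is modelled by group. This stands. The only reservation is that the scripted question is about breathing.
- **Control is not fixed at 0 of 33.** The adverse-event lists are introduced as examples, and the SOP requires all adverse events to be recorded. Under intention-to-treat, a control patient moved to NHF who could not tolerate it could also count in control. This stands, and it is why the calculation is labelled a limiting case. It does not remove the asymmetry, because prompted recording in two arms and unprompted recording in the third is still differential.
- **No biased test is specified.** The item can be read as descriptive safety information on the investigational device, and it serves the 60 versus 40 L/min comparison, where both arms are prompted alike. This is a fair reading, but the plan does not state it, and the general Fisher sentence has no exception.
- **Discomfort-driven crossover counts as treatment failure.** The general definition is arm-neutral. It captures only patients who change treatment, and the detailed list names the move from NHF to the mask but not the reverse.
- **The case report form is not in the available text.** It may already prompt for mask discomfort. That cannot be checked, and the protocol's own instruction does not ask for it.

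**Conclusion.** The point holds in a limited form. The event-type item is named for NHF only, in both its definition and its collection instruction, and as written it cannot support a between-arm statement against control. The direction of bias is against NHF.

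The size depends on an intolerance rate that the documents do not give and on how much general recording captures in control. With equal true rates and no capture, the pooled false-positive chance runs from about 2% at 5% intolerance to 97% at 20%; with partial capture it is lower. It also depends on the item being tested by arm, which only the general Fisher sentence would bring about.

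The primary outcome, the sample size and the three-arm VAS comparison are unaffected. Importance is minor, because this is one clause of an additional outcome, but the correction is cheap.

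**What to change.** In Additional outcome 4 and in the data-collection section, replace the reference to NHF or HFNC with: related to the assigned oxygen device (NHF cannula, Venturi mask or nonrebreathing mask). Record the same yes/no item in all three arms at the existing follow-up time points. Note the device in use each time, since NHF patients move to a Venturi mask on weaning. Reword secondary outcome 4 so that tolerance refers to the support modality, as the two descriptions of VAS collection already do.

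If the item is to stay NHF-only, state in the Statistical Analysis Plan that it is descriptive, may be compared only between the 60 and 40 L/min arms, and is excluded from any test against control.

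The cost is a wording change and one extra case report form entry per time point: at most 15 per patient (baseline, 1 and 2 hours, then 12 four-hourly points from 4 to 48 hours). No treatment rule and no sample size changes.
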